15.5. Contraception Requirements

All women of childbearing potential and all men must ensure that highly effective contraception is used during the study and for 6 months (24 weeks) after their last dose of study treatment. In addition, participants should not donate sperm or eggs for the duration of the study and for at least 5 times the half-life of BIIB092 or 6 months, whichever is longer, after their last dose of study treatment.

For the purposes of this study, women who do not meet one of the following criteria are considered to be physiologically capable of becoming pregnant and are, therefore, defined as women of childbearing potential:

- Postmenopausal:
 - 12 continuous months of natural (spontaneous) amenorrhea without an alternative medical cause and a serum FSH level >40 mIU/mL at Screening Visit 1.
 - 6 weeks after surgical bilateral oophorectomy with or without hysterectomy.
- Posthysterectomy.
- Female surgical sterilization (e.g., bilateral tubal ligation).

For the purposes of the study, highly effective contraception is defined as use of 2 of the following:

CONFIDENTIAL

The information contained herein may not be used, disclosed, or published without the written consent of Biogen MA Inc.

For female participants:

- Established use of oral, intravaginal, or transdermal combined (estrogen and progestogen containing) hormonal methods of contraception associated with the inhibition of ovulation.
- Established use of oral, injected, or implanted hormonal methods of contraception.
- Placement of an intrauterine device or intrauterine hormone-releasing system.
- Barrier methods of contraception with use of a spermicide, including condom, nonprescription sponge, or occlusive cap (diaphragm or cervical vault cap) used with spermicidal foam, gel, film, or cream suppository.
- Sex with a male who has undergone surgical sterilization (with the appropriate postvasectomy documentation of the absence of sperm in the ejaculate).

For male participants:

- Vasectomy with negative semen analysis at follow-up.
- Condoms with spermicide.
- Sex with a woman who uses the methods described for females if she is of childbearing potential.

For all participants, true abstinence, when this is consistent with the preferred and usual lifestyle of the participant, can be considered an acceptable method of contraception based on the evaluation of the Investigator who should also take into consideration the duration of the clinical study. Periodic abstinence (e.g., calendar, ovulation, symptothermal, postovulation methods) and withdrawal are not considered acceptable methods of contraception.

Pregnancy reporting is described in Section [15.4.1](#).

15.6. Safety Responsibilities

15.6.1. The Investigator

The Investigator's responsibilities include the following:

- Monitor and record all AEs, including SAEs, on the CRF regardless of the severity or relationship to study treatment, [REDACTED].
- Determine the seriousness, relationship to study treatment, [REDACTED], and severity of each event.

CONFIDENTIAL

The information contained herein may not be used, disclosed, or published without the written consent of Biogen MA Inc.

- Determine the onset and resolution dates of each event.
- Monitor and record all pregnancies in female participants and follow up on the outcome of all pregnancies.
- Complete an SAE form for each SAE and fax or email it to Biogen within 24 hours of the study site staff becoming aware of the event.
- Pursue SAE follow-up information actively and persistently. Follow-up information must be reported to Biogen within 24 hours of the study site staff becoming aware of new information.
- Ensure all AE and SAE reports are supported by documentation in the participants' medical records.
- Pursue AE follow-up information, if possible, until the event has resolved or become stable. Record AE follow-up information, including resolution, on the CRF, as applicable.
- Report SAEs to local ethics committees, as required by local law.

15.6.2. Biogen

Biogen's responsibilities include the following:

- Before a study site can enroll any participants, the Clinical Monitor is responsible for reviewing with study site staff the definitions of AE and SAE, as well as the instructions for monitoring, recording, and reporting AEs and SAEs.
- Biogen is to notify all appropriate regulatory authorities, central ethics committees, and Investigators of SAEs, as required by local law, within required time frames.

CONFIDENTIAL

The information contained herein may not be used, disclosed, or published without the written consent of Biogen MA Inc.

16. STATISTICAL METHODS AND DETERMINATION OF SAMPLE SIZE

The objectives of the study and the endpoints to be analyzed are listed in Section 6.

16.1. General Considerations

Data will be collected and analyzed separately for the placebo-controlled period and LTE period:

1. After the placebo-controlled period is completed, efficacy and safety analyses will be performed.
2. Analyses will be performed as needed during the LTE period. Descriptive statistics will be used to evaluate the long-term safety and efficacy data of BIIB092.

Summary statistics will be presented. For continuous endpoints, summary statistics will generally include: number of participants with data, mean, SD, median, and range. For categorical endpoints, this will generally include: number of participants randomized or dosed, number of participants with data, and the percentage of those with data in each category. Data for participants who were randomized to BIIB092 low dose (125 mg once every 4 weeks or 375 mg once every 12 weeks) will be pooled for statistical testing and modeling for efficacy, PD, and health outcome analyses, unless otherwise specified in the placebo-controlled period. All statistical tests will be 2-sided.

Similar analyses will be applied to both the placebo-controlled and LTE periods, except for efficacy analyses, which will be detailed in the statistical analysis plan (SAP).

16.2. Demography and Baseline Disease Characteristics

Demographics and baseline data will be summarized by treatment group with summary statistics or with frequency distributions.

16.3. Safety

16.3.1. Analysis Population

The population for safety analyses is defined as all participants who were randomized and who received at least 1 dose of study treatment.

16.3.2. Methods of Analysis

16.3.2.1. Adverse Events

All analyses of AEs will be based on the principle of treatment emergence. An AE is considered to be treatment emergent if it has an onset date on or after the date of first dosing, or if it was

CONFIDENTIAL

The information contained herein may not be used, disclosed, or published without the written consent of Biogen MA Inc.

present prior to the first dose and subsequently worsened. The incidence of all AEs will be presented by system organ class and preferred term by dose group and for the overall active treatment group. In addition, the incidence of all AEs will be presented by severity, by relationship to study treatment, [REDACTED].

16.3.2.2. Clinical Laboratory Results

Clinical laboratory evaluations include hematology, blood chemistry, and urinalysis evaluations. Analyses of clinically significant abnormalities, shifts from baseline to postbaseline relative to the normal range, as well as changes from baseline by visit, will be presented by dose group and for the overall active treatment group.

16.3.2.3. Vital Signs

The analysis of vital signs will focus on clinically relevant abnormalities, which will be defined in more detail in the SAP. The incidence of clinically relevant abnormalities in vital signs will be summarized by dose group and for the overall active treatment group.

16.3.2.4. Electrocardiograms

The analysis of ECG data will focus on clinically relevant abnormalities, which will be defined in more detail in the SAP. ECG changes from baseline may be summarized using descriptive statistics and presented by dose group, overall active treatment group, and visit.

16.3.2.5. Physical and Neurological Examinations

Abnormal findings during physical and neurological examinations will be recorded as AEs and will be reflected in the summary of AEs.

16.3.2.6. Columbia - Suicide Severity Rating Scale

C-SSRS data will be summarized using descriptive statistics and presented by dose group and for the overall active treatment group.

16.4. Efficacy

16.4.1. Analysis Population

Efficacy analyses will use the intent-to-treat (ITT) population, defined as all participants who were randomized and who received at least 1 dose of study treatment. For each endpoint, additional conditions may apply to the definition of the population for the analysis. Participants will be analyzed in the groups to which they were randomized. Subgroup analysis may be done for selected endpoints (e.g., CDR-SB).

CONFIDENTIAL

The information contained herein may not be used, disclosed, or published without the written consent of Biogen MA Inc.

16.4.2. Methods of Analysis

16.4.2.1. Analysis of Primary Efficacy Endpoint (Clinical Dementia Rating Scale – Sum of Boxes)

The CDR-SB is the primary efficacy endpoint. The population for the analysis of CDR-SB will be participants in the ITT population who have a baseline and at least 1 postbaseline CDR-SB score.

A mixed model with repeated measures (MMRM) will be used to analyze changes from Baseline in CDR-SB using fixed effects of treatment, time, treatment-by-time interaction, baseline CDR-SB, baseline CDR-SB-by-time interaction, region, disease stage (MCI versus mild AD), and baseline AD medication use. The correlation between repeated measures of the outcomes will be taken into consideration. The least-squares (LS) means, the differences in LS means between each treatment group versus placebo at Weeks 24, 52, and 78, 95% confidence intervals (CIs), and p-values will be presented. Changes from baseline in CDR subscores will be analyzed in a similar model. Additional details will be provided in the SAP.

The multiple comparison procedure modelling (MCP-MOD) method will be used to assess and model dose-response relationships (potential candidate models will include linear, linear-log, quadratic, maximum response [E_{max}], and logistic models as specified in Section 16.10) while controlling for multiplicity. The dose-response parameter of interest for MCP-MOD will be the LS means at Week 78 for each dose group from the mixed-effects model. Pairwise comparisons of each BIIB092 dose group versus placebo will also be conducted.

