16.4.2.2. Analysis of Exploratory Clinical Endpoints

The clinical endpoints assessing AD progression from Baseline include the results of the MMSE, ISLT, DKEFS, DSST, Trails A, eCog, ADCS-ADL, FAQ, ADAS-Cog 13, and NPI-10.

These clinical endpoints will be analyzed using data from participants in the ITT population who have a baseline and at least 1 postbaseline score for the specific endpoint being analyzed. As these are exploratory endpoints in this study, no additional multiplicity adjustment procedures will be applied to the analyses of these endpoints.

An MMRM approach will be used to analyze changes from baseline using fixed effects of treatment, time, treatment-by-time interaction, baseline score, baseline score-by-time interaction, region, disease stage (MCI versus mild AD), and baseline AD medication use. The correlation between repeated measures of the outcomes will be taken into consideration. The LS means, the differences in LS means between each treatment group versus placebo at Weeks 24, 52, and 78, and the 95% CIs and p-values will be presented.

Exploratory analysis may be performed to develop a composite cognitive score participants with MCI due to AD and/or participants with mild AD.

CONFIDENTIAL

The information contained herein may not be used, disclosed, or published without the written consent of Biogen MA Inc.

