16.10. Sample Size Considerations

There was no formal sample size calculation for the primary endpoint of safety.

The planned sample size is 528 participants, randomized in a 1:1:2:2 ratio, with 88 participants assigned to the BIIB092 low-dose group (44 assigned to 125 mg once every 4 weeks and 44 assigned to 375 mg once every 12 weeks), 88 participants assigned to the medium-dose group (600 mg once every 4 weeks), 176 participants assigned to the high-dose group (2000 mg once every 4 weeks), and 176 participants assigned to the placebo group. This sample size provides approximately 80% power to detect a dose-response relationship in the change from baseline in CDR-SB (primary efficacy endpoint) at 18 months (Week 78), assuming a mean change of 1.99 from baseline in CDR-SB at 18 months in the placebo group and a common SD of 2.38, a maximal 40% reduction for the highest BIIB092 dose group compared with the placebo group, and an estimated 20% dropout rate at 18 months (Week 78) in this study. Six different dose-response relationships will be tested at the 2-sided 5% significance level, using the MCP-MOD method to control for multiplicity [Bretz 2005]. Optimal contrasts will be constructed to detect potential dose-response trends under common dose-response curves (e.g., Emax, exponential, logistic, linear in log dose, and quadratic model) which are illustrated with the parameters shown in Figure 2.

The mean and SD of the change from baseline in CDR-SB at 18 months for the placebo group is based on available Alzheimer’s Disease Neuroimaging Initiative (ADNI) data from ADNI 1, ADNI 2, and [REDACTED].

[REDACTED]

[REDACTED]

[figure not shown]
[REDACTED]

CONFIDENTIAL

The information contained herein may not be used, disclosed, or published without the written consent of Biogen MA Inc.

In the LTE period, the actual sample size, [REDACTED], is dependent on the enrollment rate, and thus, sample size calculation is not needed.

Figure 2: Dose-Response Shapes Based on Clinical Dementia Rating Scale – Sum of Boxes Mean Change from Baseline at Week 78

ED₅₀ = median effective dose; Emax = maximum response

Note: This figure was generated using ADDPLAN[®] DF Version 3.1.8, by Aptiv solutions.

CONFIDENTIAL

The information contained herein may not be used, disclosed, or published without the written consent of Biogen MA Inc.

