4.1 LTE interim analyses at PC period database lock

The LTE interim analyses (IA) will be performed at the PC period database lock after the last patient out in the PC period. All the efficacy analyses described in [Section 5.3](#) will be performed with available efficacy data up to week 104 at the PC period database lock. Given the timeline of scheduled data collection, only a few subjects will have tau PET, CSF biomarker and health outcomes data collected in LTE visits. No LTE analyses of tau PET, biomarker or health outcomes will be included at LTE IA at PC period database lock.

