5.3.2 Method of Analysis

5.3.2.1 Considerations for base MMRM model for change from baseline analyses

A mixed model with repeated measures (MMRM) will be used to analyze changes from baseline in a parameter of interest using fixed effects of LTE treatment group, visit (categorical), LTE treatment group-by-visit interaction, baseline of the parameter of interest, baseline of the parameter of interest-by-visit interaction, region (Japan and Australia will be combined), baseline MMSE, baseline disease stage, and baseline AD symptomatic medication use. The correlation between repeated measures of the outcomes will be taken into consideration. An unstructured covariance matrix will be used to model the within-subject variance-covariance errors. If the unstructured covariance structure matrix results in a lack of convergence, the heterogeneous first-order autoregressive covariance structure followed by the heterogeneous Toeplitz covariance structure will be used. The least-squares (LS) means, the differences in LS means between each LTE treatment group versus placebo at each visit, 95% confidence intervals (CIs), and p-values will be presented. In the primary analysis of each endpoint, missing data are assumed to be missing at random [Rubin 1976].

For the LTE interim analysis at PC DBL, only records up to week 104 will be included in the MMRM model.

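### The protocol's Week 78 models leave out baseline MMSE, which every participant has and the LTE SAP adjusts for; the likely cost is a small loss of precision, unless the separate placebo-controlled SAP already adds it

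*Protocol*

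**What the plan says.** Protocol 16.4.2.1 specifies an MMRM for change in CDR-SB. Besides treatment, time and treatment-by-time, the fixed effects are "baseline CDR-SB, baseline CDR-SB-by-time interaction, region, disease stage (MCI versus mild AD), and baseline AD medication use". The Week 78 LS means from this model are also the input to MCP-MOD. The section leaves further detail to the SAP.

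Protocol 16.4.2.2 uses the same structure for the exploratory scales: "baseline score, baseline score-by-time interaction, region, disease stage (MCI versus mild AD), and baseline AD medication use".

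The LTE SAP, section 5.3.2.1, has the same skeleton but ends the list with "region (Japan and Australia will be combined), baseline MMSE, baseline disease stage, and baseline AD symptomatic medication use". Its output includes "the differences in LS means between each LTE treatment group versus placebo at each visit". Section 5.3.1 defines the late-start group as everyone randomized to placebo, whether or not they entered the LTE. Section 3.4 uses the placebo-controlled baseline for analyses spanning both periods, and Appendix I, Table 1 gives CDR analysis visits at Weeks 24, 52 and 78 as well as later ones. On timing, section 4.1 says: "The LTE interim analyses (IA) will be performed at the PC period database lock after the last patient out in the PC period".

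The LTE SAP's Introduction states that a separate SAP covers the placebo-controlled period. That SAP is not among the documents.

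**The concern.** MMSE is part of inclusion criterion 5 and is scheduled for everyone at Screening Visit 1 (protocol 8.1 and Table 1), so the covariate should be essentially complete and costs nothing to use. The sponsor already adjusts for it in the LTE model. If baseline MMSE predicts decline beyond baseline CDR-SB, disease stage and AD medication use, omitting it leaves explainable variance in the residual. Confidence intervals at Week 78 are then wider than they need be, and the MCP-MOD test loses a little power.

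There is also a consistency issue. Followed as written, the two documents produce a Week 78 high-dose versus placebo contrast from the same arms at the same lock under different adjustment, and the LTE SAP does not say what status its Week 78 contrast has.

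**Working it through.** **Inputs (protocol 16.10 unless noted).** 528 planned at 1:1:2:2, so 176 each on high dose and placebo; 20% dropout; "assuming a mean change of 1.99 from baseline in CDR-SB at 18 months in the placebo group and a common SD of 2.38"; at most 40% less decline in the top dose group than on placebo; 2-sided 5%. 654 were randomized (protocol 7.1).

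**1. Reproduce the plan's figure.** The claim is: "This sample size provides approximately 80% power to detect a dose-response relationship in the change from baseline in CDR-SB". For high dose versus placebo:
- n = 176 × 0.8 = 140.8 per arm
- effect = 0.40 × 1.99 = 0.796
- SE = 2.38 × √(2/140.8) = 0.284
- z = 0.796/0.2837 = 2.806
- power = Φ(2.806 − 1.960) = 80.1%

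The figure reproduces with no MMSE adjustment. For MCP-MOD the Figure 2 parameters are not shown. Two assumed sets of six shapes gave 80% to 86% per shape and 83% on average, also consistent with the claim.

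**2. Add baseline MMSE.** The documents do not say how much variance it explains. Assume a partial R² of 1% to 6%, given the covariates already in the model. The new SE is SE × √(1 − R²).

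| N randomized | R² | SE | SE reduction | z | Power, high dose vs placebo |
|---|---|---|---|---|---|
| 528 | 0 | 0.2837 | – | 2.806 | 80.1% |
| 528 | 1% | 0.2822 | 0.5% | 2.820 | 80.5% |
| 528 | 6% | 0.2750 | 3.0% | 2.894 | 82.5% |
| 654 | 0 | 0.2549 | – | 3.123 | 87.8% |
| 654 | 1% | 0.2536 | 0.5% | 3.139 | 88.1% |
| 654 | 6% | 0.2471 | 3.0% | 3.221 | 89.6% |

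The 654 rows assume that the same allocation and dropout apply: 654/3 × 0.8 = 174.4 per arm.

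In participants, N/(1 − R²) − N gives about 5 to 34 at 528 and 7 to 42 at 654. MCP-MOD moves similarly: under one assumed set of shapes at 528, average power goes from 83.1% to 83.4% at a partial correlation of 0.10 (R² 1%) and to 85.4% at 0.25 (R² 6.25%).

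**3. How far apart would the two Week 78 estimates be?** From MMSE alone, the difference has SD = SE × √R²: 0.2837 × 0.100 = 0.028 points at R² 1%, and 0.2837 × 0.245 = 0.069 at 6%, against a planned effect of 0.796.

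**4. Is MMSE the only difference?** No. The LTE model combines Japan and Australia, which the protocol does not state, and at the interim it takes records up to Week 104. In an illustrative simulation with assumed variances, the added Week 104 records shifted the Week 78 estimate with SD 0.016 when 3% of those with a Week 104 record had missed Week 78, 0.025 when 8% had, and 0 when none had.

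**The case against.** **The governing document is missing.** Protocol 16.4.2.1 defers detail to the SAP, and a placebo-controlled SAP exists. It may already include baseline MMSE, in which case no precision is lost. This stands, and the point is conditional on it.

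**The gain is small and its size is assumed.** This also stands. Entry restricts MMSE to 22 to 30, and baseline CDR-SB, its interaction with time, disease stage and medication use are already in the model. Both favour the low end of the range. With 654 randomized, power is about 88% without MMSE.

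**The protocol model is valid as it is.** Adjusting for the baseline score and the named stratification factors is standard. Omitting one more prognostic covariate neither biases the randomized comparison nor inflates its type I error. This stands; the change is an improvement, not the repair of an error.

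**A stronger reading to avoid.** A reader might infer that one database lock gives two rival Week 78 p-values with nothing to say which counts, and might add an error rate for claiming success on either. The documents do not support that. Protocol 16.4.2.1 designates its own model for the primary efficacy endpoint and for MCP-MOD. LTE SAP 5.3.3 makes Week 104 the primary comparison of the LTE interim analysis, and CDR-SB in the LTE is exploratory (protocol section 6; LTE SAP 2.2). No text allows the LTE model to support a Week 78 claim, so an either-test error rate describes a rule the plan does not contain. What remains is that the LTE table would print Week 78 contrasts with p-values and no label.

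**Adding MMSE would not make the two results identical.** Correct, as step 4 shows. Protocol 16.4.3 also limits the LTE analysis to participants dosed in the LTE; the overlap of arms rests on the LTE SAP's use of the full analysis set.

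**Conclusion.** The point holds in a limited form. The protocol's lists in 16.4.2.1 and 16.4.2.2 omit a covariate that is collected in everyone and that the LTE SAP uses for the same arms. Provided the placebo-controlled SAP does not already add it, and MMSE explains 1% to 6% of the remaining Week 78 variance, the cost at 528 is 0.4 to 2.4 points of power for high dose versus placebo. At 654 it is about 0.3 to 1.9 points (87.8% to between 88.1% and 89.6%). The plan's figure of approximately 80% is met without MMSE. The mismatch with the LTE model is a matter of alignment and labelling.

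**What to change.** 1. Add baseline MMSE to the fixed effects in protocol 16.4.2.1 and 16.4.2.2, or confirm that the placebo-controlled SAP already has it and bring the protocol list into line. When MMSE is the outcome, enter its baseline once only; LTE SAP 5.3.2.1 needs the same proviso, because it lists both the outcome's baseline and baseline MMSE.
2. Use one region coding in the protocol, the placebo-controlled SAP and the LTE SAP: Japan and Australia combined everywhere, or nowhere.
3. State in the LTE SAP that its Week 24, 52 and 78 contrasts are descriptive, and that the 16.4.2.1 model is the sole source of Week 78 inference. Small differences will remain because the LTE model includes records after Week 78; the label deals with these.

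The cost is a few phrases and one more model term, with no new data or participants. It should be settled before the placebo-controlled data are unblinded.
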